1.2 Background therapeutic information

Atorvastatin Mechanism of Action and Pharmacokinetics

Atorvastatin is a synthetic lipid-lowering agent, and not a pro-drug, but delivered in its active form as the calcium salt of the active hydroxyl acid at oral administration. Atorvastatin is a selective, competitive inhibitor of 3-hydroxy-3-methylglutharyl-coenzyme A reductase (HMGCR) that catalyzes the conversion of HMG-CoA to mevalonate, which is an early and rate-limiting step in the biosynthesis of cholesterol. Of importance for the abilities of atorvastatin to diffuse across membranes, the acid form consists of a lipophilic part and a more hydrophilic part. In humans, the acid form is converted to a lactone form, which is more lipophilic compared with the acid form. The formation of the active metabolites from the acid and the lactone is mediated through CYP3A4.

Atorvastatin is rapidly absorbed after oral administration; maximum plasma concentrations occur within 1 to 2 hours. Atorvastatin tablets are 95-99% bioavailable compared to solutions. The absolute bioavailability is around 14%, whereas the systemic bioavailability of HMGCR inhibitory effect is approximately 30%. The relatively low systemic bioavailability depends on the pre-systemic clearance in the gastrointestinal-tract and/or hepatic first-passage-metabolism. Mean distribution of atorvastatin is approximately 565 L. Atorvastatin is 98% bound to plasma proteins. Approximately 70% of circulating inhibitory activity for HMGCR is attributed to active metabolites. Elimination is predominantly via biliary excretion, whereas the renal route is less important. Mean plasma elimination half-life of atorvastatin is 7 hours, however, the elimination half-life of the inhibitory activity for HMGCR is 20 to 30 hours due to the contribution of longer-lived active metabolites. Atorvastatin can be administrated either as a morning or an evening dose. Apart from grapefruit, food is not considered to affect the extent of absorption. Grapefruit is a CYP3A4 inhibitor, and similarly, pharmaceutical CYP3A4 inhibitors, such as erythromycin and itraconazole can interact with atorvastatin.

Clinical studies, atorvastatin

In phase I trials the tolerated dose of atorvastatin for life-long treatment is soundly documented from cardiovascular studies and doses up to 80 mg per day are generally well tolerated. In phase II trials, atorvastatin is a well-documented drug and regularly used in humans, and large trials enrolling thousands of patients have demonstrated a high degree of safety and tolerability. The side effects of atorvastatin are few, with the most important being:

- 1) Hepatic effects raising serum transaminases, although not associated with other clinical signs or symptoms.
- 2) Muscle effects in terms of myopathy in conjunction with elevated creatinine phosphokinase values. Rhabdomyolysis has been reported in very rare cases, and renal dysfunction secondary to myoglobinuria has been reported.

Pharmaceutical Data, atorvastatin

Supplied: Atorvastatin retrieved from the hospital-pharmacy by the study nurse and provided to the patient.

Stability: Good.

Storage: Normal indoor temperature.

Solution Preparation: Tablets.

Route of Administration: Orally administrated.

Cholesterol-related side effects, aromatase inhibitors

In an adjuvant trial, hypercholesterolemia was reported in 52.3% of letrozole-treated patients and 28.6% of tamoxifen-treated patients. Grade 3-4 hypercholesterolemia was reported in 0.4% of letrozole patients and 0.1% of tamoxifen patients. Also, in the adjuvant setting, an increase of \geq 1.5 X ULN in total cholesterol (generally non-fasting) was observed in patients on monotherapy who had baseline total serum cholesterol within the normal range (i.e., \leq 1.5 X ULN) in 151/1843 (8.2%) on letrozole

vs 57/1840 (3.2%). Lipid lowering medications were required for 25% of patients on letrozole and 16% on tamoxifen.

2 OBJECTIVES OF THE TRIAL

2.1 Primary objective

The primary objective of this trial is to determine the clinical efficacy of (neo)adjuvant atorvastatin as measured by invasive disease-free survival (IDFS) among patients with primary breast cancer.

2.2 Secondary objectives

Secondary objectives embrace investigating additional clinical endpoints including: pathological response (only neo-adjuvant treated patients), recurrence-free survival, distant-recurrence-free interval including associations with first site of recurrence, and overall survival and cardiac death-free interval as well as comorbidity, overall safety and patient reported outcome.

Additional translational objectives (described in the translational protocol part) include molecular biological predictors of (neo)adjuvant treatment - including atorvastatin - in breast cancer patients will be studied based on tumor tissue and circulating markers of response to atorvastatin will be correlated with the clinical response.

For patients already on cholesterol-lowering medication, who are included in the observational non-randomized cohort among which prospective data and biological samples are collected, the objective is to evaluate breast cancer prognosis among non-randomized breast cancer patients on cholesterol-lowering medication as "real world data" and include information on prevalent use.

2.3 Endpoints

Primary endpoint:

Invasive disease-free survival (IDFS), defined as the time from randomization until the date of the first occurrence of one of the following events:

- Ipsilateral invasive breast tumor recurrence: invasive breast cancer involving the same breast parenchyma as the original primary.
- Regional invasive breast cancer recurrence: Invasive breast cancer in the axilla, regional lymph nodes, chest wall, and skin of the ipsilateral breast.
- Distant recurrence: Metastatic disease-breast cancer that has either been biopsy confirmed or clinically diagnosed as recurrent invasive breast cancer.
- Death attributable to any cause, including breast cancer, non-breast cancer, or unknown cause.
- Contralateral invasive breast cancer.
- Second primary non-breast invasive cancer.

Secondary endpoints:

- A. Pathological response (only neo-adjuvant treated patients)
- B. Distant-recurrence free interval defined as time from inclusion to first distant recurrence including associations with first site of recurrence.
- C. Recurrence-free interval including associations with first site of recurrence
- D. Overall survival.
- E. Overall safety.
- F. Cardiac death-free interval. Cardiac death is defined as:
 - a. Definitive cardiac death due to heart failure, myocardial infarction or documented primary arrhythmia.

- b. Probable cardiac death defined as sudden, unexpected death within 24 hours of a definite or probable cardiac event (e.g., syncope, cardiac arrest, chest pain, infarction, arrhythmia) without documented etiology.
- G. Co-morbidity incidence beyond cardiac events during follow-up including diagnoses such as diabetes mellitus.
- H. Patient reported outcome.
- I. Translational endpoints covering i.e.:
 - a. Baseline tumor- and circulating biomarkers predicting clinical response to atorvastatin
 - b. Alterations of circulating lipid-associated biomarkers (i.e. cholesterol, LDL, HDL, triglycerides, ApoA, and ApoB) and the association with clinical response to atorvastatin.
 - c. Alterations of circulating hormone biomarkers (*e.g.*, estradiol) and the association with clinical response to atorvastatin.

All statistical clinical endpoint analyses will be performed for the entire study population as well in exploratory analyses separately for:

- neoadjuvant and adjuvant treated patients in order to detect a potential differentiated effect of statin depending on the time of systemic therapy.
- patients receiving combined systemic therapy with chemotherapy, anti-HER2 therapy, and/or endocrine therapy AND endocrine-only treated patients.
- pre- and postmenopausal patients.

As for the randomized cohort, patients included in the observational cohort will be analyzed separately in supplemental analyses according to corresponding endpoints as specified above. In additional analyses, patients enrolled in the observational cohort will be analyzed as a third treatment arm together with the two randomized arms (atorvastatin treated, and placebo treated) and constitute information on the effects of statin use as "real world data".

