6.4 After the end of treatment (follow-up)

The follow-up includes assessment of clinical events (recurrences) and overall survival at a yearly basis up to 10 years after inclusion in the study. Patients are followed in the clinic according to the time points for clinical routine visits (up to 10 years depending on menopausal status). Clinical events are recorded at a yearly basis into the DBCG CRF database.

To ensure detection of potential long-term effects and side effects of STUDY TREATMENT, linkage to medical records and the national cancer - and death registries up to 20 years after diagnosis will facilitate long-term follow-up and detection of late recurrences and other secondary cancers. Other possible late side effects will be identified through linkage to the Hospitalization Registry.

Importantly, patient reported outcomes are to be reported yearly through a RedCap-based model up to 10 years after study inclusion.

6.5 Summary table 1

Study procedures for the randomized cohort described in the following table:

Required Investigations	Baseline (T1)	3 months (+/- 14 days) (T2)	6 months (+/- 14 days) (T3)	1 year (+/- 14 days) (T4)	2 years (+/- 14 days) (T5)	Yearly, (+/- 28 days) 3-10 years (T6)
Inclusion - exclusion criteria (DBCG)	X					
Informed consent	X					
Randomization (DBCG)	X					
CRF Master flow (DBCG)	X	X ³	x ³⁴	X ³⁴	X ³⁴	X ⁴
CRF Master AE (DBCG)	X	X ³⁴	X ³	X ³⁴	X ³	
STUDY MEDICATION START/ADHERENCE (DBCG)	X	Х	Х	Х	Х	
Patient Reported Outcome (RedCap)	X	X	X	X	X	X
Pathological response (Only patients in neo- adjuvant cohort)			Х			
HCG⁵(serum or urine)	X					
Hepatic (ALT) function	X ²	Х		Х	Х	
Renal (creatinine) function	X ²					
Creatine kinase ¹	(X)					
Translational blood samples	X		(X neoadjuvant cohort patients)	X	X	
Translational tumor tissue samples from existing tissue	X		(X neoadjuvant cohort patients)			

^{1.} Predisposing factors for rhabdomyolysis, including hypothyroidism, reduced renal function, any muscle – or liver disease, or excessive alcohol consumption above 14 drinks/week AND creatine kinase (CK) measured to more than five times the upper limit (CK only measured in case of predisposing factors).

- 2. Blood samples are allowed to be taken up to 28 days before T1
- 3. Either done by phone interview or attendance at the clinic
- 4. Data collected from the patient file
- 5. Only fertile women

6.6 Summary table 2

Study procedures for the observational cohort are described in the following table:

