8 STATISTICAL CONSIDERATIONS

8.1 Statistical design

8.1.1 Sample size

Design

A multi-center randomized placebo-controlled double-blind phase III trial investigating the effects of atorvastatin on breast cancer in the (neo)adjuvant setting.

Sample size

The sample size calculations are based on estimates of 10-year IDFS with an annual hazard rate of 0.0223. A sufficient number of patients is sought to provide 80% power using a two-sided 0.05-level test to detect a 25% reduction in the risk of an IDFS event (hazard ratio=0.75). A total of 379 events are required. With an estimated 5% drop-out at 5 years (annual rate 0.0103), this is estimated to be achieved by a total recruitment of 3,360 participants and a $6\frac{1}{2}$ years follow-up. The sample size estimate is based on inclusion for 3 years, a median follow-up of $6\frac{1}{2}$ year, that is 5 years of additional follow-up after the 3 years of inclusion.

Hypothesis

H0: (Neo)adjuvant atorvastatin treatment has no impact on invasive disease-free survival for breast cancer patients and survival rates do not differ between randomized groups; atorvastatin versus placebo.

Ha: Atorvastatin treatment influence invasive disease-free survival in breast cancer.

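### The primary endpoint counts every second non-breast invasive cancer without excluding basal-cell and squamous-cell skin carcinoma, which modestly dilutes the IDFS comparison

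*Protocol*

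**What the plan says.** Section 2.3 of the protocol makes IDFS a time-to-first-event composite, "defined as the time from randomization until the date of the first occurrence of one of the following events". The last item on the list is "Second primary non-breast invasive cancer". The efficacy assessments in the synopsis give the same item. Neither place carries a qualifier, and basal-cell and squamous-cell carcinoma are mentioned nowhere in the protocol. Skin enters the endpoint only as a site of regional breast cancer recurrence.

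Section 8.1.1 sizes the trial to "provide 80% power using a two-sided 0.05-level test" and to "detect a 25% reduction in the risk of an IDFS event (hazard ratio=0.75"). The control rate comes from "estimates of 10-year IDFS with an annual hazard rate of 0.0223", and "A total of 379 events are required". The hazard ratio of 0.75 is therefore stated for the whole composite.

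The clinical evidence in section 1.1 reports recurrence, breast-cancer-free interval and distant-recurrence-free interval. Section 6.4 adds long-term follow-up through "linkage to medical records and the national cancer - and death registries up to 20 years after diagnosis", partly to find other secondary cancers.

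**The concern.** Basal-cell and squamous-cell skin carcinomas are invasive cancers outside the breast. Under the list as written, each one ends a patient's IDFS time as an event. Nothing in the protocol's rationale suggests that atorvastatin should prevent them. Events on which the drug has no effect occur at the same rate in both arms and move the composite hazard ratio toward 1. The trial then has less power than its sample-size section states, unless the 0.75 already allows for them.

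The list is complete and appears twice, so this is a rule the protocol states and not a detail it leaves open. An exclusion that appeared only in a later document would change the endpoint as the protocol words it. The protocol is therefore the right place to settle the question.

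**Working it through.** **Inputs from the protocol (section 8.1.1):** control hazard 0.0223 per year; hazard ratio 0.75; two-sided 0.05; 80% power; 379 events; 3,360 patients, 1:1 (1,680 per arm); 3 years of accrual plus 5 years of follow-up. On dropout the section says "With an estimated 5% drop-out at 5 years (annual rate 0.0103").

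**Assumptions, not in the protocol:** skin carcinoma rate m of 0.001 to 0.003 per year; hazard ratio 1.0 on these lesions and 0.75 on all other IDFS events; constant hazards; uniform accrual.

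**Step 1: reproduce the plan.** Required events (Schoenfeld) = 4(1.960 + 0.842)² / (ln 0.75)² = 379.4, which matches 379.

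With h = λ + 0.0103, the probability that a patient has an event by the cutoff is

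p(λ) = (λ/h) × [1 − (e^(−5h) − e^(−8h)) / (3h)].

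- Control: λ = 0.0223, h = 0.0326, p = 0.1304, so 1,680 × 0.1304 = 219.1 events.
- Atorvastatin: λ = 0.75 × 0.0223 = 0.016725, h = 0.027025, p = 0.0996, so 167.3 events.
- Total 386 events. Power = Φ(√386.3/2 × |ln 0.75| − 1.960) = Φ(2.827 − 1.960) = 80.7%.

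The stated design is reproduced.

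**Step 2: add the skin carcinomas on top of 0.0223.** The control hazard becomes 0.0223 + m and the atorvastatin hazard 0.016725 + m. The composite hazard ratio is their quotient. For m = 0.001 it is 0.017725 / 0.0233 = 0.761.

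| m per year | Composite HR | Events at 3+5 years | Of which skin | Power at 3+5 years | Power at exactly 379 events |
|---|---|---|---|---|---|
| 0 | 0.750 | 386 | 0 | 80.7% | 80.0% |
| 0.001 | 0.761 | 405 | 20 | 78.6% | 75.9% |
| 0.002 | 0.771 | 423 | 39 | 76.5% | 71.8% |
| 0.003 | 0.780 | 442 | 59 | 74.4% | 67.8% |

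At the planned schedule the extra events offset part of the dilution, so the loss is about 2 to 6 percentage points. Excluding the lesions restores 80.7%.

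**Step 3: the alternative, in which 0.0223 already includes them.** The control hazard stays at 0.0223, and the atorvastatin hazard is 0.75 × (0.0223 − m) + m.

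| m per year | HR, counted | Events, counted | Power, counted | Events, excluded | Power, excluded |
|---|---|---|---|---|---|
| 0.001 | 0.761 | 389 | 76.7% | 370 | 79.0% |
| 0.002 | 0.772 | 391 | 72.3% | 354 | 77.2% |
| 0.003 | 0.784 | 393 | 67.7% | 337 | 75.2% |

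Exclusion gives more power here too, but from fewer events.

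**Step 4: how many later events are masked.** Take an arm with other-event hazard b and a patient with potential follow-up T. The chance of a skin carcinoma first and another IDFS event before T is the integral over u from 0 to T of m·e^(−(m+b+0.0103)u) × b/(b+0.0103) × [1 − e^(−(b+0.0103)(T−u))]. Averaging over T from 5 to 8 years and adding both arms (1,680 patients each) gives 1.2, 2.5 and 3.7 patients for the three rates, so about 1 to 4 of 3,360.

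**The case against.** The strongest reply is that the protocol does not contradict itself. There is one event list, and the 0.75 is stated for that list. The protocol never assumes 0.75 for breast cancer events alone. The split into 0.75 for other events and 1.0 for skin cancers belongs to this check. Section 1.1 cites estimates from 0.64 to 0.76, so 0.75 may already leave some room for unresponsive events. This stands: the documents do not show that the 80% was derived for a narrower endpoint.

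The size also rests on a rate that the protocol does not give, and on no drug effect on these lesions. That stands too, and it is why only a range is shown.

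Three stronger readings are tempting but not supported:

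- **Power of 76-68%.** This holds only if the analysis were fixed at exactly 379 events. Section 8.2 times the initial analysis by follow-up, and the protocol states no event trigger.
- **Material masking of breast recurrences.** Few patients are affected, nothing stops follow-up at a second cancer, and the recurrence-free and distant-recurrence-free intervals still count a later recurrence.
- **Registry linkage will bring these lesions into the primary analysis.** Section 6.4 presents the linkage as long-term follow-up. It does not say that the cancer registry feeds IDFS, or that these sources record every such lesion.

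It can also be said that other second cancers and non-breast deaths may dilute in the same way, and that a SAP could define which lesions qualify. The first is true but does not argue for keeping a component outside the rationale. The second does not remove the problem, because the protocol states the list without restriction.

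**Conclusion.** The point holds in a limited form. As written, basal-cell and squamous-cell skin carcinomas are primary-endpoint events, and the protocol gives no reason to expect atorvastatin to reduce them. With 1 to 3 such cancers per 1,000 patient-years on top of 0.0223 and no drug effect on them, the IDFS hazard ratio goes from 0.75 to about 0.76-0.78 and power at the planned follow-up from about 81% to 79-74%. If 0.0223 already includes them, power is 77-68% when they are counted and 79-75% when they are excluded, so exclusion helps under either reading. The direction follows from the definition and the no-effect assumption. The size depends on the assumed rate. This is a modest loss of power that can be avoided; it does not threaten the validity of the trial.

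**What to change.** In section 2.3 and in the synopsis efficacy assessments, extend the item to read: "Second primary non-breast invasive cancer", *excluding basal-cell and squamous-cell carcinoma of the skin*. Make the change while the trial is blinded. Keep recording these lesions outside IDFS, as adverse or co-morbidity events.

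The cost is one clause in two places and slightly fewer IDFS events per year. The sponsor should check whether the source of the 0.0223 hazard counted these lesions. If it did, the expected number of events should be restated: under the assumed rates, about 370 to 337 at the planned schedule against the 379 required. If the sponsor means to count them, the protocol should say so and justify 0.75 for that composite.

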3 PATIENT SELECTION CRITERIA

3.1 Inclusion criteria

- ♦ Women with primary, estrogen receptor positive breast cancer who are candidates for (neo)adjuvant systemic therapy OR have received ≤3 years of adjuvant endocrine therapy.
- ◆ Age > 18 years.
- ♦ Performance status of ECOG \leq 2.
- Prior to patient registration, written informed consent must be given according to ICH/GCP, and national/local regulations.

3.2 Exclusion criteria

- History of any prior (ipsi- and/or contralateral) invasive breast carcinoma
- Prevalent cholesterol lowering therapy (statins, fibrates, ezetimibe, PCSK9 inhibitors). These
 patients can be enrolled in the observational cohort given fulfillment of other in- and exclusion
 criteria.
- Evidence of hepatic dysfunction (alanine aminotransferase level more than three times the upper limit of the normal range) or renal dysfunction (creatinine level more than three times the upper limit of the normal range).
- Predisposing factors for rhabdomyolysis, including hypothyroidism, reduced renal function, any muscle – or liver disease, or excessive alcohol consumption above 14 drinks/week AND creatine kinase (CK) measured to more than five times the upper limit (CK only measured in case of predisposing factors).

- ♦ Current medication with potent CYP3A4-inhibitors (e.g. ketokonazole, erythromycin) or gemfibrozile, ciclosporin or danazol.
- Pregnancy or breast-feeding (contraception according to clinical routines for premenopausal, fertile breast cancer patients, that includes non-hormonal contraception such as condom, vaginal diaphragm, or intrauterine device).
- Psychological, familial, sociological or geographical condition potentially hampering compliance with the study protocol and follow-up schedule; these conditions will be discussed with the patient before registration in the trial.
- History of allergic reactions attributed to compounds of similar chemical or biological composition to atorvastatin.

4 TRIAL DESIGN

A multi-center randomized 1:1 placebo-controlled, double-blind phase III trial investigating the effects of atorvastatin on breast cancer in the (neo)adjuvant setting.

5 THERAPEUTIC REGIMENS, EXPECTED TOXICITY, DOSE MODIFICATIONS, DRUG ADMINISTRATION

5.1 Treatment plan

5.1.1 Drug administration

STUDY MEDICATION (atorvastatin, oral administration, 80 mg daily (evening) OR placebo) two years of duration starting at study enrollment and for two years onwards.

The Glostrup pharmacy will be responsible for the following regarding medication:

- 1. Buy atorvatastin 80 mg (TEVA)
- 2. Produce the placebo medication
- 3. Create documentation for the Medical Product Agency (catalogue scheme)
- 4. Randomization list in collaboration with the DBCG secretary
- 5. Be responsible for labelling and packing (in glasses of 100 tablets/glas) of both active medication (atorvastatin 80 mg) and placebo
- 6. Distribution to all trial sites

Control of receiving of STUDY MEDICATION:

Glostrup Apotek ensures that the temperature range is adhered to when dispatching test drugs. This is ensured through the use of Distributor (BHS Logistics) who works under the rules of Good Distribution Practice. When dispatching medication, enclose a receipt for receipt stating the quantity delivered. The medication received is checked against this receipt, which is signed and returned to Glostrup Pharmacy. Furthermore, the medicine delivered must be compared with what has been ordered. This should be described in a short instruction, where everyone who receives the medicine must have completed this instruction, thus ensuring proper training in the function.

